### **8.6.2 Statistical Methods for Efficacy Analyses**

Clinical responses will be listed for subjects in Part A for both the MK-4280 monotherapy arm and the MK-4280 in combination with pembrolizumab arm by dose level.

For the secondary endpoint of ORR, the point estimate and 95% CI will be evaluated separately in Part B subjects treated with MK-4280 monotherapy, in combination with pembrolizumab (separately for co-formulated product or following sequential administration), and in combination with pembrolizumab and either mFOLFOX7, FOLFIRI or lenvatinib at the RP2D for each tumor cohort separately, using an exact method based on binomial distribution (Clopper-Pearson interval).

A comparison will be conducted for ORR between the 2 doses of MK-4280 in combination with pembrolizumab administered in the gastric cancer cohort. Miettinen and Nurminen's

method will be used to estimate the treatment difference between the 2 doses and its 95% CI. Other exploratory endpoints may also be compared between doses (eg, DOR, PFS). Data from subjects who experienced disease progression in the Part B monotherapy gastric arm and crossed over into the combination arm will be summarized separately and will not be included in the dose comparison analysis.

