## 4.2 Rationale

### 4.2.1 Rationale for the Trial and Selected Subject Population

MK-4280 is being developed for treatment of solid tumors. This trial is the first-in-human (FIH) trial designed to assess the safety, tolerability, antitumor efficacy, PK, and pharmacodynamics of escalating doses of MK-4280 alone and in combination with pembrolizumab with or without chemotherapy or lenvatinib in subjects with advanced solid tumors. The specific tumor types for Part B were selected based on the expression of LAG-3, the known response rates to anti-PD-1/PD-L1 monotherapy in these tumor types, unmet medical need, and preliminary efficacy data observed in Part A of the study.

HNSCC was chosen based on high expression of LAG-3, and known response to PD-1 therapy. Both PD-1/PD-L1 inhibitor treatment-refractory (Cohort D) and naïve (Cohort C) populations are being assessed. There is scientific evidence that the expression of alternate immune checkpoints including LAG-3 may increase after PD-1 blockade, promoting resistance to PD-1 therapy [23]. Co-blockade with LAG-3 and PD-1 may overcome resistance in some tumors. The intention of the PD-1 refractory cohort (Cohort D) is to determine if MK-4280 and pembrolizumab therapy can benefit patients that have progressed on prior PD-1 therapy. The intention of the PD-1 naïve HNSCC cohort (Cohort C) is to determine if MK-4280 and pembrolizumab therapy improves upon the response rates observed with pembrolizumab monotherapy in this population. Results from Keynote-055 demonstrated an objective response rate of 18% in PD-1 naïve HNSCC patients that had progressed on at least 2 prior lines of therapy [24].

MSS CRC was chosen based on high expression of LAG-3, little to no responsiveness to PD-1 monotherapy, and high unmet medical need [25]. Response rates for regorafenib and TAS-102, approved agents in 3L CRC, have an OS benefit of 2 months compared to best supportive care and ~1-2% ORR. Regorafenib improved median OS to 6.4 months from 5.0 months, and TAS-102 improved median OS to 7.1 months from 5.3 months [26] [27]. The intention of this cohort is to determine if MK-4280 plus pembrolizumab improves on the response rates observed for 3L standard of care therapies.

Gastric cancer was chosen based on LAG-3 expression and intermediate responsiveness to PD-1 blockade with an ORR 11.2% in PD-L1 positive gastric cancer patients that had received at least 2 prior lines of therapy.

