## 8.7 Interim Analyses

In this study there will be no hypothesis testing. Safety data will be examined on a continuous basis to allow for dose-escalation and dose-confirmation decisions.

In Part B, Arm 2A of the study, an interim analysis will be performed for the CRC and PD-1-treatment-naïve HNSCC cohorts receiving MK-4280 in combination with pembrolizumab. For these tumor cohorts, after 10 subjects have been enrolled and have at least 1 post-baseline scan assessment, the ORR will be evaluated. If an individual cohort experiences an ORR of 20% or greater (ie, at least 2 of 10 subjects), this cohort will be expanded to enroll a maximum of 30 (PD-1-treatment-naïve HNSCC) or 90 (CRC) additional subjects, for a maximum of 40 or 100 subjects in the particular cohort. Enrollment to these cohorts will not be paused in the time period between when 10 subjects have been enrolled and when the interim analysis is performed. If fewer than 2 of 10 subjects experience an objective response in a given cohort, the totality of data will be evaluated to decide whether or not to continue enrollment in that cohort. The operating characteristics of the interim analysis rule are provided in [Table 10](#).

Table 10 Operating Characteristics of Interim Analysis Rule for Each Tumor Type

True ORR	Probability of $\leq 1$ of 10 Subjects Respond
10%	0.74
15%	0.54
20%	0.38
25%	0.24
30%	0.15
35%	0.09
40%	0.05
45%	0.02
50%	0.01

To aid in internal decision making, an interim analysis of efficacy may be performed comparing the 2 doses of MK-4280 in combination with pembrolizumab (Part B, Arm 2A, 2B) administered in the gastric cancer cohort after approximately 25 subjects per dose have been enrolled and have at least 1 post-baseline scan.

Additionally, if antitumor activity is observed in this cohort ( $\geq 8$  of 40 subjects with an objective response, irrespective of dose) an additional 20 subjects with gastric cancer will be enrolled to receive MK-4280 monotherapy at the RP2D. The operating characteristics of the interim analysis rule are provided in [Table 11](#). If this predetermined ORR is not observed, the Sponsor will evaluate all available data before determining whether to enroll these additional subjects or not.

Table 11 Operating Characteristics of Interim Analysis Rule for Determining Conduct of Gastric Cancer Monotherapy Cohort

True ORR for the Combination	Probability Gastric Cancer Monotherapy Cohort Conducted ( $\geq 8$ of 40 Combination Subjects Respond)

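### In Arm 2A Cohorts A and C, the fixed-N ORR pools the 10 subjects whose responses open the expansion, so after expansion by that rule the point estimate is modestly biased upward

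*Combined protocol and SAP*

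**What the plan says.** Section 8.7 sets the interim look in Arm 2A for the CRC and PD-1-naive HNSCC cohorts: "after 10 subjects have been enrolled and have at least 1 post-baseline scan assessment, the ORR will be evaluated". The rule follows: "If an individual cohort experiences an ORR of 20% or greater (ie, at least 2 of 10 subjects), this cohort will be expanded", with the ceiling "for a maximum of 40 or 100 subjects in the particular cohort". Below the threshold the outcome is left open: "If fewer than 2 of 10 subjects experience an objective response in a given cohort, the totality of data will be evaluated to decide". The same section adds: "Enrollment to these cohorts will not be paused". Sections 2.1.2 and 5.2.2.2.2 agree.

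For the final analysis, Section 8.6.2 gives each Part B cohort a point estimate and 95% CI "using an exact method based on binomial distribution (Clopper-Pearson interval"). The Full Analysis Set in Section 8.5.3 takes in every treated subject with measurable disease at baseline, so the first 10 are included. Tables 14 and 16 in Section 8.9.3 give intervals for N=40 and N=100. Section 8 contains no adjustment for the interim rule and no comment on it. The supplemental SAP is reserved for exploratory and non-confirmatory work, whereas this ORR is a secondary endpoint.

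Section 4.2.1 says what the estimates are for. The HNSCC cohort is to show whether the combination "improves upon the response rates observed with pembrolizumab monotherapy in this population", with 18% cited for pembrolizumab alone. The CRC cohort is set against approved third-line agents at about 1-2%.

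**The concern.** If a cohort reaches full size because its first 10 subjects did well enough, those 10 are no longer a neutral sample. Given that the rule was met, their expected number of responders exceeds 10 times the true rate, whatever that rate is below 100%. Pooling them with later subjects carries the excess into the reported ORR.

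These are single-arm cohorts to be read against outside reference rates, so the point estimate carries most of the message. An upward shift looks like a gain from adding MK-4280, and nothing in the planned output would tell a reader that part of the figure comes from the expansion rule.

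**Working it through.** **Inputs.** Threshold of 2 responders in 10 and final N of 40 or 100 (Section 8.7); first 10 retained (8.5.3); simple proportion with Clopper-Pearson CI (8.6.2). True ORRs of 18% and 2% come from the reference rates in Section 4.2.1. The values 5%, 10% and 30% are assumptions that span a range.

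**Reproducing the plan.** Table 10 is P(X1 ≤ 1) with X1 ~ Bin(10, p). At 10% this is 0.736 (stated 0.74); at 20% it is 0.376 (stated 0.38). All nine entries reproduce. In Tables 14 and 16, 8/40 gives 9.1% to 35.6% and 10/100 gives 4.9% to 17.6%. These and the other tabulated intervals reproduce with N taken as fixed.

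**Bias given expansion by rule.** Let X2 ~ Bin(N−10, p) be the later responders.

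- Probability that the rule is met: G = 1 − (1−p)^10 − 10p(1−p)^9
- E[X1 | X1 ≥ 2] = (10p − P(X1=1)) / G
- Bias of (X1+X2)/N = (E[X1 | X1 ≥ 2] − 10p) / N

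At p = 18%: P(X1=1) = 0.3017 and G = 0.5608, so E[X1 | X1 ≥ 2] = (1.8 − 0.3017)/0.5608 = 2.67. The bias at N=40 is (2.67 − 1.80)/40 = 2.18 points.

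| N | True ORR | G | E[X1 given rule met] | Expected pooled ORR | Bias (points) |
|---|---|---|---|---|---|
| 40 | 10% | 26.4% | 2.32 | 13.3% | +3.30 |
| 40 | 18% | 56.1% | 2.67 | 20.2% | +2.18 |
| 40 | 30% | 85.1% | 3.38 | 31.0% | +0.96 |
| 100 | 2% | 1.6% | 2.06 | 3.9% | +1.86 |
| 100 | 5% | 8.6% | 2.15 | 6.65% | +1.65 |
| 100 | 10% | 26.4% | 2.32 | 11.3% | +1.32 |

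**If some misses also expand.** Let a cohort with 0 or 1 responders expand with probability q. Then E[X1 | expanded] = (10p − (1−q)·P(X1=1)) / (G + q(1−G)). With q = 0.5 and p = 18% this is (1.8 − 0.151)/0.780 = 2.113, so the bias at N=40 is (2.113 − 1.8)/40 = 0.78 points. The same calculation gives 0.69 at N=40 and 0.28 at N=100 when p = 10%. With q = 1 the bias is zero.

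**Interval.** Given expansion by rule, two-sided coverage of the fixed-N 95% interval is at least 95% at every true ORR computed from 10% to 30%, for both sizes. It falls to 91.9% at N=40 with true 5%, and to 88.4% at N=100 with true 2%; at N=100 with true 5% it is 95.7%. The misses lean optimistic. At N=40 and true 18%, the lower limit exceeds the truth when there are 13 or more responders: 3.3% given expansion by rule, against 2.0% at fixed N.

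**Joint probability.** Expanding by rule and also having a lower limit above the truth: 0.561 × 3.26% = 1.8% at 18%, N=40 (fixed N: 2.0%); 0.086 × 4.33% = 0.4% at 5%, N=100 (fixed N: 1.1%).

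**What an adjusted estimate would show.** For S responders in all, the conditionally unbiased estimate averages (S−a)/(N−10) over a ≥ 2 with weights C(10,a)·C(N−10,S−a). An observed 8/40 (20.0%) becomes 17.9%, and 10/100 (10.0%) becomes 8.6%.

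**The case against.** The strongest reply is that this is a Phase 1b estimation study. Section 8.7 says that no hypotheses will be tested, and Section 8 contains no comparison with the 18% or 1-2% rates that the bias could corrupt. The shift is small beside the CI half-widths, about 13 points at 8/40 and 6 points at 10/100. All of that stands, and it limits how much weight the point can bear. It does not remove the bias: where estimation is the whole product, an estimate shifted by a known mechanism deserves a note, and Section 4.2.1 does declare the intention to compare.

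Some stronger readings are tempting, and the documents do not support them.

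- A reader might infer that the rule by itself manufactures an apparent gain, or makes a false gain more likely. Overall it does not: the joint probabilities above are no higher than at fixed N. At a true CRC rate of 2% the rule is met only 1.6% of the time.
- A reader might infer that the Clopper-Pearson interval is invalid. At true rates of 10% to 30% it is not materially so.
- A reader might infer that upward bias holds in every frame. If stopped cohorts are reported as well and the rule is applied strictly, the simple proportion is biased downward on average: by 3.7 points at 18% (N=40) and 3.1 points at 10% (N=100).
- A reader might infer that CRC has no estimate free of this rule. Arms 2C and 5 each enroll 40 Cohort A subjects without it, though at 800 mg, so the gap concerns the 200 mg dose.

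**Conclusion.** The point holds as a modest, conditional bias in a point estimate. For a cohort expanded by rule to full size it is about 1 to 3 points at N=40 (true ORR 10% to 30%) and 1.3 to 1.9 points at N=100 (true ORR 2% to 10%). In relative terms it matters most for CRC at a true rate of 5% or less, where the rule is seldom met.

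For the stated N these are upper bounds, since any expansion after a miss pulls the average down. They rest on three assumptions: enrollment reaches the maximum (a smaller final N would enlarge the bias in proportion to 1/N); response at the interim look is the response counted at the end; and any discretionary expansion is unrelated to responses in later subjects. The last may fail, because enrollment continues during the look and the Sponsor reviews all available data. The plan gives no basis for quantifying that. This is a cheap improvement worth making, not a flaw that undermines the cohorts.

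**What to change.** In Section 8.6.2, for Arm 2A Cohorts A and C:

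1. Keep the pooled ORR and its Clopper-Pearson CI.
2. Beside it, state the interim rule and whether the cohort expanded by rule or by Sponsor discretion.
3. Add one prespecified sensitivity estimate: either the ORR and Clopper-Pearson CI in subjects enrolled after the first 10 (up to 30 and 90), or a two-stage conditionally unbiased estimate.
4. Show that estimate alongside any comparison with the 18% or 1-2% reference rates.

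The cost is a few lines of SAP text and a little analysis, with no new data. The second-stage interval is wider: at an observed 20%, 6/30 gives 7.7% to 38.6% against 9.1% to 35.6% for 8/40 (about 16% wider), and 18/90 is about 6% wider than 20/100. Resting every benchmark statement on the later subjects alone would set aside 10 of 40 HNSCC subjects. That is a trade-off the plan need not make, which is why the added estimate is a sensitivity analysis and not a replacement.

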Randomization Ratio	In Part A and all cohorts of Part B besides the gastric cancer cohort (Cohort E), subjects are allocated to their particular treatment arm without randomization. In Cohort E of Part B, subjects are randomized at a 1:1 ratio to 1 of 2 doses of MK-4280 (200 mg [Arm 2A] or 700 mg [Arm 2B]) in combination with a fixed dose of pembrolizumab. Allocation to Arm 3 or Arm 4 will be guided by a subject's eligibility for one arm or the other or, if eligible for both arms, will be determined by investigator choice. If Arms 1, 2C and 5 for 3L+ CRC subjects are enrolling at the same time, subjects will be assigned in an alternating fashion across the open arms at the study level through IVRS. Cohort F of Part B is only open to sites in China and these subjects will be assigned to Arm 5 only.

A list of abbreviations used in this document can be found in Appendix 12.6.

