#### **5.2.2.2.4 Dose Finding in Subjects With Gastric Cancer (Arm 2A and 2B)**

Subjects with gastric cancer (Cohort E) of Part B will be randomized 1:1 via an IVRS/IWRS to either the preliminary RP2D from Part A (200 mg, Arm 2A) or 700 mg (Arm 2B) dose level of MK-4280 in combination with a fixed dose of pembrolizumab to more thoroughly assess differences in activity and safety/tolerability of these doses. However, if the TPI portion of Part B calls for a de-escalation of the RP2D, these doses will be modified accordingly, and the decision to modify these doses will be communicated to sites via an administrative letter before enrollment into this cohort begins.

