### **8.4.1 Efficacy/Immunogenicity/Pharmacokinetics Endpoints**

Objective response rate in subjects treated with MK-4280 alone, in combination with pembrolizumab, or in combination with pembrolizumab and either mFOLFOX7, FOLFIRI or lenvatinib is a secondary endpoint of the trial and is defined as the proportion of subjects in the analysis population who experience complete response (CR) or partial response (PR) using RECIST 1.1 criteria as assessed by investigator review. Other efficacy endpoints (eg, Duration of Response [DOR], progression-free survival [PFS], Overall Survival [OS]) or the use of irRECIST 1.1 criteria are exploratory endpoints in this trial and will be defined in the sSAP.

Pharmacokinetic endpoints include serum concentrations of MK-4280, pembrolizumab, and lenvatinib, and derived PK parameters.

For the comparison of MK-4280 and pembrolizumab pharmacokinetics administered as a co-formulated product (MK-4280A, Cohort A, Arm 5) with that of its individual components administered sequentially (Cohort A, Arm 2C), the pharmacokinetic endpoints of interest are  $AUC_{0-21\text{days}}$  and  $C_{\max}$  from the first cycle. Additional PK parameters such as  $AUC_{0-\infty}$  and soluble LAG-3 exposure parameters such as  $AUC_{0-21\text{days}}$  from the first cycle administration of MK-4280A and MK-4280 administered in sequential combination with pembrolizumab are also of interest.

To characterize the pharmacokinetics in subjects from China, pharmacokinetic endpoints include serum concentrations of MK-4280 and pembrolizumab, and derived PK parameters:

- Single dose parameters:  $AUC_{0-21\text{days}}$ ,  $C_{\max}$ ,  $T_{\max}$ , and  $t_{1/2}$ .

- Multiple dose parameters:  $C_{trough}$ ,  $AUC_{0-21days}$ , and  $C_{max}$  at steady state, accumulation ratio.

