#### **8.5.3 Efficacy Analysis Populations**

The FAS population will be used for the analysis of secondary and exploratory efficacy data in this trial. The FAS population consists of all subjects with a baseline scan with measurable

disease by investigator assessment who were administered a dose of study treatment regardless of dose level.

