## **8.6 Statistical Methods**

This Section describes the statistical methods that address the primary and secondary objectives. Methods related to exploratory endpoints will be described in the sSAP.

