### 8.9.3 Efficacy Expansion

**Table 14**, **Table 15** and **Table 16** show the ORR estimate and the 95% CI (Clopper-Pearson interval) for various sample sizes among the Part B expansion cohorts or additions to cohorts under protocol amendments.

Table 14 Estimate and 95% CI of ORR (N=40)

Number of Responses (PR/CR)	Observed ORR	95% CI of ORR
3	7.5%	(1.6%, 20.4%)
4	10.0%	(2.8%, 23.7%)
5	12.5%	(4.2%, 26.8%)
6	15.0%	(5.7%, 29.8%)
7	17.5%	(7.3%, 32.8%)
8	20.0%	(9.1%, 35.6%)
9	22.5%	(10.8%, 38.5%)
10	25.0%	(12.7%, 41.2%)
11	27.5%	(14.6%, 43.9%)
12	30.0%	(16.6%, 46.5%)
13	32.5%	(18.6%, 49.1%)
14	35.0%	(20.6%, 51.7%)

Number of Responses (PR/CR)	Observed ORR	95% CI of ORR
15	37.5%	(22.7%, 54.2%)
16	40.0%	(24.9%, 56.7%)

Table 15 Estimate and 95% CI of ORR (N=60)

Number of Responses (PR/CR)	Observed ORR	95% CI of ORR
5	8.3%	(2.8%, 18.4%)
6	10.0%	(3.8%, 20.5%)
7	11.7%	(4.8%, 22.6%)
8	13.3%	(5.9%, 24.6%)
9	15.0%	(7.1%, 26.6%)
10	16.7%	(8.3%, 28.5%)

Table 16 Estimate and 95% CI of ORR (N=100)

Number of Responses (PR/CR)	Observed ORR	95% CI of ORR
8	8.0%	(3.5%, 15.2%)
9	9.0%	(4.2%, 16.4%)
10	10.0%	(4.9%, 17.6%)
11	11.0%	(5.6%, 18.8%)
12	12.0%	(6.4%, 20.0%)
13	13.0%	(7.1%, 21.2%)
14	14.0%	(7.9%, 22.4%)
15	15.0%	(8.6%, 23.5%)
16	16.0%	(9.4%, 24.7%)

Though no hypothesis testing will be performed, with 40 subjects per dose level in the gastric cancer cohort, the study has 80% power to detect a ~30% difference in ORR (for example, 55% versus 25%) at alpha=5% (1-sided) between 2 dose levels.

In the Part B MK-4280 monotherapy arms (Arm 1), 20 subjects will be enrolled in each cohort (CRC and gastric, if conducted). If the true ORR is either 5% or 10% for a given cancer type, then the chance of observing at least 1 responder among the 20 subjects will be 64% or 88%, respectively. For each cohort, if there are 0 responses, then there is 88% power to rule out a true ORR >10%.

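### Section 8.6.2 permits duration of response to be compared between the randomised gastric doses; that contrast is confined to responders and can, though need not, favour the less active dose

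*Combined protocol and SAP*

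**What the plan says.** The gastric cohort is the only randomised part of the trial. Section 1.0 states: "In Cohort E of Part B, subjects are randomized at a 1:1 ratio to 1 of 2 doses of MK-4280". Section 5.2.2.2.4 gives the purpose as "to more thoroughly assess differences in activity and safety/tolerability of these doses".

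The committed between-dose efficacy analysis in Section 8.6.2 is the ORR difference with a 95% CI by the Miettinen and Nurminen method. The next sentence is "Other exploratory endpoints may also be compared between doses (eg, DOR, PFS".

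Three other statements frame that sentence:

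- Section 8.4.1: "Other efficacy endpoints (eg, Duration of Response [DOR], progression-free survival [PFS], Overall Survival [OS]) or the use of irRECIST 1.1 criteria are exploratory endpoints". It leaves their definitions to the sSAP.
- Section 8.6: "Methods related to exploratory endpoints will be described in the sSAP".
- Section 8.5.3: "The FAS population will be used for the analysis of secondary and exploratory efficacy data in this trial".

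The documents supplied do not say how non-responders would enter a DOR comparison. They do not limit DOR to description within each dose, and they name no all-subject measure of durability.

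**The concern.** Under its usual definition DOR starts at a complete or partial response, so a non-responder has no value. A between-dose DOR contrast therefore selects subjects on something that happened after randomisation and that the dose may have changed. If the doses have the same ORR and the same kind of responders, little is lost. If ORR differs, which is what the cohort is there to detect, the two responder groups are no longer comparable by randomisation.

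A more active dose may convert additional subjects whose responses are short. Its average DOR then falls even though no subject did worse. A reader of that summary could take the less active dose to be the more durable one. PFS, named in the same sentence, is defined for every subject and does not have this problem.

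**Working it through.** **Inputs from the documents.** Section 8.9.3 gives the sample size ("with 40 subjects per dose level in the gastric cancer cohort") and the illustrative rates ("the study has 80% power to detect a ~30% difference in ORR (for example, 55% versus 25"), at 5% one-sided. It states no figure for DOR.

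**The plan's own figure.** The exact power of a one-sided Fisher test at 55% v 25% with 40 per dose is 80.9%, which agrees with the stated 80%. (The pooled normal approximation without continuity correction gives 87.5%.) The power statement is not in dispute.

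**Who would be compared.** Taking all 40 per dose to be in the FAS, expected responders are 0.55 × 40 = 22 and 0.25 × 40 = 10. The other 80 − 32 = 48 subjects (60%) would have no DOR.

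**Model (assumed; the documents give no durations).** 25% of subjects would respond at either dose, with mean DOR 12 months on both. A further 30% respond only at the more active dose, with mean DOR *m* months. Nobody does worse on the more active dose.

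- Responders-only mean DOR, more active dose: (25 × 12 + 30 × *m*) / 55. Less active dose: 12.
- Mean time in response per subject, non-responders at zero, more active dose: 0.25 × 12 + 0.30 × *m*. Less active dose: 0.25 × 12 = 3.0.

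| *m* (months) | Responders-only mean DOR, more v less active | Mean time in response per subject, more v less active |
|---|---|---|
| 4 | 420/55 = 7.6 v 12.0 | 3.0 + 1.2 = 4.2 v 3.0 |
| 6 | 480/55 = 8.7 v 12.0 | 3.0 + 1.8 = 4.8 v 3.0 |
| 9 | 570/55 = 10.4 v 12.0 | 3.0 + 2.7 = 5.7 v 3.0 |
| 12 | 660/55 = 12.0 v 12.0 | 3.0 + 3.6 = 6.6 v 3.0 |

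The responders-only difference equals (30/55) × (*m* − 12). It is against the more active dose for *m* below 12, zero at 12, and in its favour above 12. The per-subject difference is 0.30 × *m*, which is positive for every *m*.

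**With sampling error.** Simulation: 10,000 trials, 40 per dose, exponential DOR, no censoring, trials without a responder on one of the doses set aside. Here durations are set as medians: 12 months for those who respond at either dose, and the value shown for the extra responders.

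| Extra responders' median (months) | Observed median DOR longer on the less active dose | One-sided 5% log-rank in responders favours the less active dose | Total time in response, all subjects, favours the more active dose |
|---|---|---|---|
| 4 | 87% | 28% | 76% |
| 6 | 77% | 19% | 84% |
| 9 | 63% | 9% | 92% |
| 12 | 51% | 5% | 96% |

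The 55% v 25% pair is only a power example, so lower rates were tried with an extra-responder median of 6 months. The less active dose has the longer observed median, and is favoured by the log-rank, in 66% and 11% of trials at 11.2% v 20%, 69% and 14% at 15% v 30%, and 71% and 14% at 10% v 25%. The 11.2% is the gastric PD-1 rate cited in Section 4.2.1; the other rates are assumptions.

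**The case against.** The strongest reply is that the plan commits to very little here. The sentence says such endpoints may be compared and gives DOR as an example. The definition and methods are deferred to the sSAP, which is not among the documents and may keep DOR descriptive or count non-responders. No hypothesis testing is planned, and the committed comparison, ORR in the FAS, counts every non-responder. All of that stands and keeps the point small. It does not remove it, because the permission is written into Section 8.6.2 without restriction.

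The direction is also not known. A reversal needs the extra responders to have shorter responses than the others, and the documents do not indicate whether they would. That stands too.

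A reader might infer that the DOR contrast would mislead dose selection, or that 60% of the randomised subjects are left out of the dose comparison. The documents support neither.

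- No section bases dose choice on DOR. Section 4.2.3.3 bases future dosing strategy on PK with pharmacodynamic, safety and antidrug-antibody results.
- The optional gastric interim in Section 8.7, meant for internal decisions, refers to efficacy without naming DOR.
- Section 5.2.2.2.5 and Table 3 show that the sponsor has since added 800 mg, which Part B Arms 1, 2C, 3, 4, 5 and 6 use.
- The 60% applies to one optional summary, not to the ORR comparison.

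Finally, time in response with non-responders at zero depends partly on ORR, which is already compared, and it needs a horizon and censoring rules. That is a fair limit on the alternative. For this reason the alternative is needed only if durability is to be compared at all.

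**Conclusion.** The point holds as a low-priority clarification. Section 8.6.2 permits an optional exploratory DOR contrast between the randomised gastric doses. Under the usual definition that contrast is not protected by randomisation when ORR differs, and it can favour the less active dose.

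At the plan's illustrative rates, with assumed mean durations of 12 months and of 4 to 9 months for the extra responders, DOR on the more active dose looks 1.6 to 4.4 months shorter (12.0 − 10.4 and 12.0 − 7.6). Mean time in response per subject is 1.2 to 2.7 months longer (4.2 − 3.0 and 5.7 − 3.0). The conclusion rests on the usual definition of DOR, on an ORR difference, and on the extra responses being shorter. Without the last of these there is no reversal. The ORR comparison, its stated power and the PFS comparison are unaffected.

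**What to change.** In Section 8.6.2, and carried into the sSAP, drop DOR from the examples of endpoints compared between doses and state that it is summarised descriptively by dose in responders.

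If durability is to be compared between doses, use an all-subject measure in the Cohort E FAS, alongside PFS. Two candidates are mean time in response over a stated common horizon with non-responders at zero, and the probability of being in response over time.

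The cost is a wording change and one extra exploratory analysis, with a horizon and a censoring rule to state. The resulting measure is partly driven by ORR and should be read with it. The 9-weekly imaging in Section 7.1.2.8 already supplies the data, so no change to assessments, sample size or conduct is needed.
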